### **Per-Protocol (PP) Dataset:**

A subset of the mITT dataset and includes subjects who completed the study without important (or major) protocol deviations that are considered to impact data integrity (e.g., non adherence to study group assignment).

If it is determined that a subject was pregnant during the study, all of the pregnant subject's data will be reported, but will be excluded from summarization and statistical analyses.

## 6. STUDY GROUP AND PRODUCT DESCRIPTIONS

The following products will be tested in this study:

Product A: Subject's OB Cigarette (Reference Product)

Product B: Oral tobacco-derived nicotine chews marketed as VERVE® Discs Blue Mint (~1.5 mg nicotine/piece) (Test Product)

Product C: Oral tobacco-derived nicotine chews marketed as VERVE® Discs Green Mint (~1.5 mg nicotine/piece) (Test Product)

Product D: Oral tobacco-derived nicotine chews marketed as VERVE® Chews Blue Mint (~1.5 mg nicotine/piece) (Test Product)

Product E: Oral tobacco-derived nicotine chews marketed as VERVE® Chews Green Mint (~1.5 mg nicotine/piece) (Test Product)

The following groups will be tested in this study and the group descriptions will be used in the footnotes for listings, tables, and figures:

GROUP 1: Continue Smoking

GROUP 2: VERVE® Discs Dual Use

GROUP 3: VERVE® Chews Dual Use

GROUP 4: VERVE® Discs Exclusive Use

GROUP 5: VERVE® Chews Exclusive Use

GROUP 6: Tobacco Cessation

Study groups will be referred to in the text as: Continue Smoking Group, VERVE® Discs Dual Use Group, VERVE® Chews Dual Use Group, VERVE® Discs Exclusive Use Group, VERVE® Chews Exclusive Use Group, and Tobacco Cessation Group.

## 7. BIOMARKER ASSESSMENT AND ANALYSIS

### 7.1 Biomarkers Sample Collection and Measurements

#### 7.1.1 Urine Biomarkers of Exposure (BOE)

##### 7.1.1.1 Urine BOE Sample Collection

24-hour urine collections for biomarkers of exposure (total NNAL, total NNN, NE, 2-AN, 4-ABP, HEMA, CEMA, S-PMA, 3-HMPMA, 3-HPMA, 2-HPMA, AAMA, GAMA, 2-MHBMA, 2-OHFle, 2-Naphthol, 1-OHPhe, mutagenicity, and 1-OHP) will be performed on Days -1, 5, and 7. Urine creatinine will be measured in each 24-hour collection and will be used to adjust the concentration values of urine biomarkers. Each 24-hour urine collection will be from approximately ( $\pm$  30 minutes) 07:00 on the scheduled day to approximately 07:00 the following day. The 24-hour urine collection begins on each scheduled day after the first morning void and any void prior to 07:00, and finishes the following morning with the last void collected at approximately 07:00 (including first morning void). Subjects will be specifically instructed to collect all urine voided, and any missed collection during the 24-hour interval will be documented as a deviation.

##### 7.1.1.2 Bioanalytical Method

Urine aliquots for NE will be shipped to Celerion Bioanalytical Services for analysis. These samples will be analyzed using validated LC-MS/MS analytical methods.

Aliquots for creatinine will be shipped to the Celerion Clinical Laboratory for analysis.

Urine aliquots for NNAL, NNN, 2-AN, 4-ABP, HEMA, CEMA, S-PMA, 3-HMPMA, 3-HPMA, 2-HPMA, AAMA, GAMA, 2-MHBMA, 2-OHFle, 2-Naphthol, 1-OHPhe, and 1-OHP will be shipped to ABF for analysis.

Mutagenicity testing will be done by Labstat.

##### 7.1.1.3 Urine Biomarker Analysis Variables

The following variables will be determined for each urine biomarker except mutagenicity testing.

- Measured concentration
- Total biomarker mass excreted per 24 hours (primary analysis variable)
- Total mass excreted per 24 hours absolute change from Baseline
- Total mass excreted per 24 hours percent change from Baseline
- Measured concentration adjusted for urine creatinine

Urine biomarker concentration values reported as below the limit of quantitation (BLQ) will be set to one-half of the limit of quantitation prior to calculating the 24-hour mass excreted. Total urine weight (g) will be collected during the study and converted to urine volume using the assumed density of 1 gram (g) equals 1 milliliter (mL).

Creatinine-adjusted concentrations will be calculated as shown in Section 7.1.1.3.2. Absolute and percent change from baseline will be calculated as shown in Section 7.1.1.3.3.

#### 7.1.1.3.1 Urine Nicotine Equivalents

NE will be calculated as the molar sum of nicotine and 5 major nicotine metabolites excreted in urine over 24 hours. Values of individual components reported as below the limit of quantitation will be set to one-half of the limit of quantitation prior use in the calculation below.

The concentration of each metabolite will first be multiplied by the 24-hour urine volume to obtain the total amount excreted in 24 hours, then divided by the molecular weight of the metabolite to obtain the total amount of each in moles. The sum in moles will then be converted to mass of NE by multiplying by the molecular weight of nicotine.

Nicotine (mg/24h)	=	nicotine concentration [ng/mL] × 24h urine volume [mL] ÷ 1000 000
Nicotine-glucuronide (mg/24h)	=	nicotine glucuronide concentration [ng/mL] × 24h urine volume [mL] ÷ 1000 000
Cotinine (mg/24 hours)	=	cotinine concentration [ng/mL] × 24h urine volume [mL] ÷ 1000 000
Cotinine-glucuronide (mg/24h)	=	cotinine glucuronide concentration [ng/mL] × 24h urine volume [mL] ÷ 1000 000
Trans-3'-hydroxycotinine (mg/24h)	=	trans-3'-hydroxycotinine concentration [ng/mL] × 24h urine volume [mL] ÷ 1000 000
Trans-3'-hydroxycotinine-glucuronide (mg/24h)	=	trans-3'-hydroxycotinine glucuronide concentration [ng/mL] × 24h urine volume [mL] ÷ 1000 000

$$\text{Nicotine equivalents (mg/24 hours)} = \frac{(\text{nicotine [mg/24h]}/162.23 \text{ [mg/mmol]} + \text{nicotine-gluc [mg/24h]}/338.36 \text{ [mg/mmol]} + \text{cotinine [mg/24h]}/176.22 \text{ [mg/mmol]} + \text{cotinine-gluc [mg/24h]}/352.34 \text{ [mg/mmol]} + \text{trans-3'-hydroxycotinine [mg/24h]}/192.22 \text{ [mg/mmol]} + \text{trans-3'-hydroxycotinine-gluc [mg/24h]}/368.34 \text{ [mg/mmol]}) \times 162.23 \text{ (mg/mmol)}}{162.23 \text{ (mg/mmol)}}$$

#### **7.1.1.3.2 Urine Biomarkers Adjusted for Urine Creatinine**

Urine creatinine concentration will also be measured in urine collections and will be used to adjust the concentration values of urine biomarkers except mutagenicity as follows:

##### **Nicotine Equivalents**

$$\text{Nicotine equivalents (mg/g creatinine)} = \frac{\text{nicotine equivalents (\mu g/mL)} \times 100}{\text{creatinine (mg/dL)}}$$

##### **Other Urine Biomarkers**

$$\text{Urine biomarker (unit2/g creatinine)} = \frac{\text{urine biomarker (unit1/mL)} \times 100}{\text{creatinine (mg/dL)}}$$

Where: if unit1 = pg, then unit2 = ng and if unit1 = ng, then unit2 =  $\mu$ g

#### **7.1.1.3.3 Urine Biomarker Change From Baseline**

Urine biomarker change from baseline will be calculated as follows, where Baseline = Day -1:

$$\text{Absolute change from baseline} = \text{Post Randomization Value} - \text{Baseline Value}$$

$$\text{Percent change from baseline (\%)} = \frac{(\text{Post Randomization Value} - \text{Baseline Value})}{\text{Baseline Value}} \times 100 \%$$

#### **7.1.1.3.4 Urine Mutagenicity**

Urine mutagenicity will be analyzed and reported by Labstat.

250 mL urine sample will be concentrated to 1 mL and used for urine mutagenicity testing. The measurement results will be reported as revertants/ $\mu$ L. The urine mutagenicity count in the 24 hour urine will be calculated as follow:

Urine mutagenicity (revertants/250 mL) = Urine mutagenicity (revertants/  $\mu$ L) x 1000

Note: the coefficient 1000 is for 1 mL = 1000  $\mu$ L. If the volume after concentration is X mL, the coefficient will be X\*1000.

Urine mutagenicity (revertants/24 hour) = Urine mutagenicity (revertants/250 mL) x urine volume/250

Note: the coefficient 250 is the volume of urine sample used for mutagenicity test. If the sample volume is XXX mL, the coefficient will be XXX.

### **7.1.2 Blood Biomarkers of Exposure**

#### **7.1.2.1 Blood BOE Sample Collection**

The blood sample for COHb will be collected 15 minutes to 45 minutes following the start of subject's in the moment subjective questionnaires (QSU-Brief, mCEQ, and Use Product Again, as appropriate) at 21:30 ( $\pm$ 30 minutes) on Days -1, 5, and 7. Subjects will abstain from product use, as appropriate, for at least 15 minutes prior to blood draw for COHb.

#### **7.1.2.2 Bioanalytical Method**

Blood samples for COHb saturation will be shipped to the Celerion Clinical Laboratory for analysis. COHb saturation will be determined using a validated spectrophotometric method at the Celerion Clinical Laboratory, Lincoln, Nebraska.

#### **7.1.2.3 Blood Biomarker Analysis Variables**

The following variables will be determined for blood COHb.

- Measured saturation (%) (primary analysis variable)
- Measured saturation (%) absolute change from Baseline
- Measured saturation (%) percent change from Baseline

Values reported as below the limit of quantitation (BLQ) will be set to one-half of the limit of quantitation for summarization and statistical analysis.

Absolute and percent change from baseline will be calculated as shown in Section 7.1.1.3.3.

### **7.1.3 Product Use Data Collection and Analysis Variables**

#### **7.1.3.1 Data Collection**

Subjects will use the assigned products or be abstinent, as per randomization. All subjects (except Group 6) will use the assigned study product *ad libitum* (except

during meals and study procedures, as appropriate) from 07:00 through 23:00. Subjects in Group 2 and Group 3 will smoke no more than 50% of their baseline CPD and will use assigned VERVE® product ad libitum except for 3 specific VERVE® product use opportunities at 11:00, 15:00, and 19:00 each day during which subjects will be asked to keep VERVE® product in their mouth for at least 10 minutes. Subjects in Group 4 and Group 5 will only use the assigned VERVE® product ad libitum except for 3 specific VERVE® product use opportunities at 11:00, 15:00, and 19:00 each day during which subjects will be asked to keep assigned VERVE® product in their mouth for at least 10 minutes. Subjects will abstain from any product use from the start of the subjective effects questionnaires administration scheduled for 21:30 ( $\pm 30$  minutes) until after the COHb sample has been collected on Days -1, 5, and 7.

The number of each product used per day (CPD and VPD, as appropriate) will be counted for each cigarette or VERVE® product used during each day in a product use period. The total duration of each VERVE® product will be the sum of product use durations during each day in a product use period. The average duration of each VERVE® product will be the average of product use durations used per use each day in a product use period.

#### **7.1.3.2 Analysis Variables**

- number of each product used per day (CPD and VPD, as appropriate)
- average duration of VERVE® product used per use each day
- total duration of VERVE® product used per day

#### **7.1.4 Subjective Effect**

##### **7.1.4.1 Data Collection**

Subjects will also complete in the moment subjective effects questionnaires, which include:

- QSU-Brief (Protocol Appendix 2) – All subjects will complete the QSU-Brief on Days -1, 1, 5, and 7 in the morning at 07:00 ( $\pm 30$  minutes) before product use, as appropriate, and at 21:30 ( $\pm 30$  minutes).
- Modified Cigarette Evaluation Questionnaire (mCEQ-C or mCEQ-V; Protocol Appendix 3) – the appropriate mCEQ will be administered at 21:30 ( $\pm 30$  minutes). All subjects will complete the mCEQ-C on Day -1. Subjects in Group 1 will also complete the mCEQ-C on Days 1, 5, and 7. Subjects in Groups 2 and 3 will complete both of the mCEQ-C and mCEQ-V on Days 1, 5, and 7. Subjects in Groups 4 and 5 will complete mCEQ-V on Days 1, 5, and 7.
- Use the Product Again questionnaire (Protocol Appendix 4) – Subjects in Groups 1 - 5 will complete the Use the Product Again questionnaire at 21:30 ( $\pm 30$  minutes) on Day 7. Subjects in Group 1 will complete Use the Product Again questionnaire for cigarettes. Subjects in Groups 2 and 3 will complete both Use the Product Again questionnaire for cigarettes and VERVE® products. Subjects

in Groups 4 and 5 will complete Use the Product Again questionnaire for VERVE® products.

#### 7.1.4.2 Analysis Variables

##### OSU-Brief

According to the literature, the factor scores for the QSU-Brief will be calculated as follows.

- Factor 1 (anticipation of pleasure from smoking): average of items 1, 3, 6, 7, and 10.
- Factor 2 (relief of nicotine withdrawal): average of items 2, 4, 5, 8, and 9.

The following variable will be determined for each factor score.

- Change from pre-product use score (07:00 ± 30 min) to post-product use score (21:30 ± 30 min), i.e. post-product use score minus pre-product use score, on each day

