- Modified Cigarette Evaluation Questionnaire (mCEQ-C or mCEQ-V; Appendix 3) – the appropriate mCEQ will be administered at 21:30 ( $\pm$  30 minutes). All subjects will complete the mCEQ-C on Day -1. Subjects in Group 1 will also complete the mCEQ-C on Days 1, 5, and 7. Subjects in Groups 2 and 3 will complete both mCEQ-C and mCEQ-V on Days 1, 5, and 7. Subjects in Groups 4 and 5 will complete mCEQ-V on Days 1, 5, and 7.

- Use the Product Again questionnaire (Appendix 4) – Subjects in Groups 1 - 5 will complete the Use the Product Again questionnaire at 21:30 ( $\pm$  30 minutes) on Day 7. Subjects in Group 1 will complete Use the Product Again questionnaire for cigarettes. Subjects in Groups 2 and 3 will complete both Use the Product Again questionnaire for cigarettes and VERVE® products. Subjects in Groups 4 and 5 will complete Use the Product Again questionnaire for VERVE® products.

Smoking will be limited to a designated area of the clinic. Subjects permitted to smoke (Groups 1, 2 and 3) will be housed separately from the subjects that exclusively use VERVE® products (Groups 4 and 5) and subjects who stop tobacco product use (Group 6). Study product use will not be permitted from 23:00 to 07:00 each day during the study. For study integrity, all smoked butts and all used VERVE® products will be collected throughout the study. Any illicit use of any tobacco- or nicotine-containing products or sharing of study products will be strictly prohibited and will be grounds for immediate termination from the study at the discretion of the Investigator.

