### **11.7 Subjective Effects**

#### *QSU-Brief*

Descriptive statistics (n, mean, SD, CV%, minimum, median, and maximum) of the response.

The factor scores for the QSU-Brief will be calculated as follows.

- Factor 1 (anticipation of pleasure from smoking): average of items 1, 3, 6, 7, and 10.
- Factor 2 (relief of nicotine withdrawal): average of items 2, 4, 5, 8, and 9.

The following variables will be determined for each factor score.

- Actual score (primary analysis variable)
- Absolute change from Baseline
- Percent change from Baseline

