### **11.9 Statistical Analysis**

Linear mixed models for ANCOVA will be used to compare the Day 5 and Day 7 biomarker values and subjective effects questionnaire scores between groups as described in the study objectives. In the statistical models, the outcome variable will be included as a dependent variable; group, and gender will be included as fixed effects; and baseline values/scores will be included as covariates. The SAS Proc Mixed procedure will be used. The LSM difference and 95% confidence interval for the LSM difference between the Test and Reference Groups will be provided.

Normality and equal variance assumptions will be tested for biomarker variables. An appropriate data transformation will be used if parametric assumptions for the distribution of above-mentioned data are markedly violated.

The statistical significance level will be 5% for two-sided testing. Adjustments for multiple comparisons will not be made.

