6. To compare subjective effects (Questionnaire of Smoking Urges – Brief [QSU-Brief] total score, responses to modified cigarette evaluation questionnaire [mCEQ] and the Use the Product Again questionnaire) among subjects who continue to smoke cigarettes, subjects with dual usage of VERVE® Chews or VERVE® Discs and cigarettes, subjects with complete switch to VERVE® Chews or VERVE® Discs, and subjects who cease from all tobacco use for 1, 5 and 7 days.
7. To characterize product use behaviors (such as: number of cigarettes per day [CPD], number of VERVE® use per day [VPD], average and total duration of VERVE® use each day).

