### **Secondary**

The secondary outcome variables are:

- 24-hour urinary total total NNN, NE, 2-AN, 4-ABP, HEMA, CEMA, S-PMA, 3-HMPMA, 3-HPMA, 2-HPMA, AAMA, GAMA, 2-MHBMA, 2-OHFle, 2-Naphthol, 1-OHPhe, mutagenicity, and 1-OHP excreted on Day 5 and Day 7.
- 24-hour urinary total NNAL excreted on Day 5.
- COHb on Day 5 and Day 7.
- QSU-Brief responses and factor scores on Day 1, Day 5, and Day 7.
- Responses to the appropriate mCEQ on Day 1, Day 5, and Day 7.
- Responses to the appropriate Use the Product Again questionnaire on Day 7.
- Product use behavior daily from Day 1 to Day 7 (i.e., CPD, VPD, and the average and total duration of VERVE® product use each day).

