### 7.2.6 Questionnaires

The responses and the factor scores from the QSU-Brief will be listed by subject, study day and collection time. Factor scores (original scores, and change from pre-use scores) will be summarized by group, day and collection time using descriptive statistics (n, n missing, mean, SD, CV%, SEM, minimum, Q1, median, Q3, maximum, and 95% CI).

The mCEQ will be considered as a 7-point scale and treated as a continuous variable. The responses from mCEQ-C or mCEQ-V and factor scores will be listed by subject and study day. The factor scores will be summarized by group and study day using descriptive statistics (n, n missing, mean, SD, CV%, SEM, minimum, Q1, median, Q3, maximum and 95% CI).

Responses to Use the Product Again questionnaire recorded as VAS scores will be treated as bipolar variable and summarized by study group, study product and category using frequency count tables. The original response VAS score and bipolar score for the Use the Product Again questionnaire will be summarized using descriptive statistics (n, n missing, mean, SD, CV%, SEM, minimum, Q1, median, Q3, maximum and 95% CI).

These analyses will be performed on the mITT dataset.

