## **7.3.3 Subjective Effects**

Similar statistical comparison analysis (defined in 7.3.1) will be preformed on QSU-brief change from pre-use score and mCEQ original scores (mCEQ-C, among Group 1, 2, and 3; mCEQ-V, among Groups 2, 3, 4, and 5). The comparisons interested for QSU-brief will be the test groups (Groups 2-5) versus the continue smoking group (Group 1) and test groups (Groups 2-5) versus the tobacco cessation Group. The comparisons interested for mCEQ-C will be the dual use groups (Groups 2-3) versus the continue smoking group (Group 1). The comparisons interested for mCEQ-V will be the dual use groups (Groups 2-3) versus the exclusive use group (Groups 4 -5) [i.e. Group 2 vs Group 4 and Group 3 vs Group 5].

This analysis will be conducted on the mITT datasets. No multiple adjustment will be performed for subject effect scores.

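### The SAP formally tests only the within-day change in QSU-Brief; the protocol makes the actual factor score the primary analysis variable, and SAP Section 9 does not list the departure

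*SAP*

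**What the plan says.** **Protocol.** Section 11.7 defines two QSU-Brief factor scores. For each it lists the "Actual score (primary analysis variable", followed by absolute and percent change from Baseline. It names no same-day change. Section 11.9 uses ANCOVA to "compare the Day 5 and Day 7 biomarker values and subjective effects questionnaire scores between groups as described in the study objectives", with baseline scores as covariates.

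**SAP objectives and outcomes.** Secondary objective 6 (SAP 2.3.2) concerns a level, the QSU-Brief total score. SAP 2.4 lists as outcomes "QSU-Brief responses and factor scores on Day 1, Day 5, and Day 7".

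**SAP analysis.** All groups complete the questionnaire at 07:00 and 21:30 on Days -1, 1, 5 and 7 (SAP 7.1.4.1). For each factor, SAP 7.1.4.2 gives one analysis variable: "post-product use score minus pre-product use score, on each day". The between-group model in 7.3.3 is run on "QSU-brief change from pre-use score and mCEQ original scores", so the mCEQ is tested as a level and the QSU-Brief is not. The two inferential QSU-Brief tables (14.2.3.1.2.1 and 14.2.3.1.2.2) report the change only. Levels appear in 7.2.6 and Table 14.2.3.1.1: "Factor scores (original scores, and change from pre-use scores) will be summarized by group, day and collection time using descriptive statistics".

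**SAP Section 9.** It describes the SAP as aligned with the protocol apart from three items: the repeated-measures model for biomarkers, and two changes for the Use the Product Again questionnaire.

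**The concern.** The protocol plans to compare how strong the urge to smoke is in each group. The SAP compares how much that urge moves between morning and evening. These are different quantities, and one cannot stand in for the other.

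The within-day change would come close to a level comparison if the groups shared a morning starting point. That is plausible on Day 1, when the 07:00 score precedes assigned product use. On Days 5 and 7 the morning score is itself an outcome of the assigned regimen, and subtracting it can remove or invert the difference that objective 6 asks about.

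At stake is the only set of between-group estimates and p-values for smoking urge. A reader could take a null result on Day 7 to mean equal urge when one group is lower all day. A reader who relies on Section 9 would not know that the tested variable differs from the protocol's.

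**Working it through.** **1. What the plan tests.** The comparisons come from SAP 7.3.3: Groups 2-5 vs Group 1 (4) and Groups 2-5 vs Group 6 (4), so 8. The days come from the table shells (1, 5 and 7), and there are two factors.

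- Planned contrasts: 8 × 3 × 2 = 48.
- Contrasts on an actual score: 0.
- Day 1, morning score before assigned use: 8 × 1 × 2 = 16.
- Days 5 and 7, morning score after assigned use or abstinence: 8 × 2 × 2 = 32.
- Against Group 6: 4 × 3 × 2 = 24. Group 6 uses no product, so a change from pre-use to post-use has no literal meaning there.

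**2. What the contrast measures.** Write E and M for the evening and morning mean scores, T for the test group and R for the reference group.

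(E_T − M_T) − (E_R − M_R) = (E_T − E_R) − (M_T − M_R)

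This is the evening group difference minus the morning group difference. If the groups differ by the same amount d at both times, the contrast is d − d = 0 for any d.

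**3. Sensitivity to the morning difference.** Hold the evening difference at −1 point (test group lower):

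| Morning difference | Tested contrast |
|---|---|
| +1 | −1 − (+1) = −2 |
| 0 | −1 − 0 = −1 |
| −1 | −1 − (−1) = 0 |
| −2 | −1 − (−2) = +1 |

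The same evening result can appear doubled, correct, absent or reversed.

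**4. Three patterns with assumed means** (1-7 scale; Group 1 at 5 in the morning and 3 in the evening, so a change of −2). The documents give no QSU-Brief means, so these show direction only.

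| Group 4 morning, evening | Group 4 change | Change contrast | Evening difference | Morning difference |
|---|---|---|---|---|
| 4, 2 | −2 | 0 | −1 | −1 |
| 3, 3 | 0 | +2 | 0 | −2 |
| 6, 3 | −3 | −1 | 0 | +1 |

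In the first row urge is lower all day and the tested contrast is zero. In the second, morning urge is lower with VERVE, yet the contrast points against it. In the third, morning urge is higher with VERVE, yet the contrast points in its favor. In the last two rows a test at 21:30 alone would also show no difference.

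**5. Can the covariate repair this?** The table shells adjust for the Day -1 value. That value is taken before assigned use begins, so it cannot remove a morning difference that arises by Day 5 or Day 7.

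**6. Overnight interval.** Protocol Design states "Study product use will not be permitted from 23:00 to 07:00 each day during the study". The 07:00 score therefore reflects overnight abstinence in every group, and on Days 5 and 7 also the preceding days of the assigned regimen.

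**The case against.** The best defense is that the change score is a legitimate, pre-specified variable. It asks what happens to urge over a day of use after the overnight break, it is stated openly in 7.1.4.2, 7.3.3 and the table titles, and the protocol defers statistical detail to the SAP. That stands: the variable is worth keeping, and nothing is concealed. But deferring detail does not cover replacing a variable that the protocol labels primary for this questionnaire. Section 9 also reports two changes to another questionnaire, so changes of this kind were treated as reportable.

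A second defense is that levels can be read from Table 14.2.3.1.1, with 95% confidence intervals by group. This stands in part. An all-day difference would be visible there. Those intervals describe each group separately, though; they are not between-group differences, and they are not adjusted for baseline and gender as protocol 11.9 plans.

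A third is that a replacement test at 21:30 alone would have its own blind spot. This is correct, as the second and third patterns above show. A reader might infer that 21:30 is the time the protocol intends. Neither protocol 11.7 nor objective 6 restricts the comparison to the evening, so both times should be tested where they are informative.

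A reader might also count the missing total score as a further SAP departure. It is not one: protocol 11.7 defines only the two factors and the protocol's own outcome list has no total, so the mismatch with objective 6 is inherited from the protocol.

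**Conclusion.** The point holds for one secondary questionnaire. The SAP replaces the tested QSU-Brief variable without declaring it, and objective 6 is left with no formal between-group comparison of urge level. That part rests on the text alone. The cancellation in 32 of the 48 contrasts is algebra, but whether any of the 32 is distorted in practice depends on the Day 5 and Day 7 morning group differences, which cannot be known from the documents.

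Two stronger readings are not supported. A reader might infer that the QSU-Brief results will be wrong or biased toward the test products; the documents give no means, SDs or correlations to show this, and the distortion can go either way. A reader might also infer that the main conclusion is at risk; the primary endpoint is Day 7 NNAL, and its analysis does not use this questionnaire.

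The change should be made before database lock. It does not call the design into question.

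**What to change.** - In SAP 7.1.4.2 and 7.3.3, add the actual Factor 1 and Factor 2 scores as tested variables, using the 7.3.1 model: at 21:30 on Days 1, 5 and 7, and at 07:00 on Days 5 and 7. Use the Day -1 score at the same time of day as covariate. State why the Day 1 morning score is left out (it precedes assigned use).
- Keep the within-day change as a supportive analysis.
- List the choice of QSU-Brief variables in Section 9.
- Either define the total score named in objective 6, or align objective 6 with the factor scores in SAP 2.4. Each factor averages five of the ten items, so a mean-scored total is (5·F1 + 5·F2)/10 = (F1 + F2)/2 and adds little.

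**Cost.** SAP wording, one line in Section 9, matching table shells, and four secondary models (two factors × two times of day) on data already collected. The added contrasts are 8 × 3 × 2 = 48 in the evening and 8 × 2 × 2 = 32 in the morning, 80 in all, unadjusted for multiplicity as 7.3.3 already provides. If no group differences existed, about 80 × 0.05 = 4 would reach the 5% level by chance, so they should be reported as secondary and read together. Testing a total score as well would add 8 × 5 = 40.
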